## Hypotheses and Objectives:

The purpose of this study is to investigate the effect of Walkasins (Figure 1), a new user-friendly and robust external lower limb sensory prosthesis developed by RxFunction Inc. under NIH funding through a Small Business Innovative Research grant, on the balance and gait of persons with peripheral neuropathy who also experience balance problems. Walkasins provide gentle vibrations to the skin around the lower leg that reflect changes in pressure under the foot sole indicating the state of balance. The user learns to use these vibrations to control balance.

We hypothesize that patients who use the Walkasins turned on will receive balance information that will improve their outcomes on gait and balance function, whereas patients who wear Walkasins turned off will not improve their outcomes on gait and balance function.

**Figure 1. The Walkasins incorporate a thin shoe insert that measures changes in foot pressure during body sway. Vibrations provided to the skin on the lower calf represent new sensory information that the patient learns to use to improve balance.**

PROTOCOL XXXX-X

The Effect of Walkasins on Balance and Gait in People with Peripheral Neuropathy

PI: [name]

Version Date: April 5, 2016

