- 10 meter Gait Speed – The 10m-walk (Perera, Mody et al. 2006) is routinely done in rehabilitation, has excellent reliability in chronic stroke patients (Hiengkaew, Jitaree et al. 2012) and physical therapists are well- trained in reliably performing this measure. In addition, gait speed has been found to be an important predictor of survival in older adults (Hardy, Perera et al. 2007), further emphasizing its importance as a clinical outcomes measure. Gait speed (10 meter walk using the middle 6 meters) will be assessed under two conditions: 1) instructed to walk at normal speed, 2) instructed to walk as fast as they can. A difference of 0.10m/sec is defined as the minimal clinically important difference (MCID) (Perera, Mody et al. 2006).

PROTOCOL XXXX-X

The Effect of Walkasins on Balance and Gait in People with Peripheral Neuropathy

PI: [name]

Version Date: April 5, 2016

- **4-Stage Balance Test** – The 4-Stage Balance Test is part of the CDC recommended test protocol for balance function (STEADI, [http://www.cdc.gov/steady/pdf/4-stage\\_balance\\_test-a.pdf](http://www.cdc.gov/steady/pdf/4-stage_balance_test-a.pdf)). It includes four gradually more challenging postures the subject is exposed to; 1) Stand with feet side by side; 2) Stand with feet in semi-tandem stance; 3) Stand with feet in tandem stance; 4) Stand on one leg. Subjects pass if they can hold the stance for 10 s and then move on to the next stance. A fail of 1, 2 or 3 indicates at risk of falling. In addition we will record time for each of the tests.

Subjects will then be randomized into two groups according to their gait function (as measured by the FGA) and use of an assistive device (normal use is permitted, but not during the research study). Group A will initially be trained and tested with the Walkasins turned on, then following a 60 minute break, will be trained and tested with the Walkasins turned off. Group B will initially be trained and tested with the Walkasins turned off, then following a 60 minute break, will be trained and tested with the Walkasins turned on. During testing, subjects will complete trials of Functional Gait Assessment, 10 meter Gait Speed and the 4-Stage Balance Test. All training and testing will be done by a physical therapist.

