### **Data Analysis:**

The primary outcome measures of this study include the Functional Gait Assessment, 10 meter Gait Speed test, and the 4-Stage Balance Test. Using a between-group parametric statistical model, we will compare baseline measures from both groups to post-training outcomes following the first training session. We expect that Group A (i.e., the group that first trained with the Walkasins on) will have a statistically significant improvement in functional gait and balance measures compared to Group B (i.e., the group that first trained with the Walkasins off). We will also compare baseline measures to the post-training outcomes for Group A following the second training session (i.e., with the Walkasins off) to confirm that the 60 minute break between training sessions allowed for a washout effect of the first training. If we are able to confirm a washout effect, we will pool our data (n=30) to compare the outcome measures from baseline and post-training with the Walkasins turned on.

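### The conditional pooled step (n=30) compares device-on scores with the pre-training baseline, not with the device-off post-training scores, so practice and therapist training count as device effect

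*Combined protocol and SAP*

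**What the plan says.** Under Research Methodology, every subject is tested three times: at baseline (device worn but off, before any training), after the first training session, and after the second. Group A goes on then off. For the other sequence, "Group B will initially be trained and tested with the Walkasins turned off, then following a 60 minute break", training and testing are repeated with the device on. The same kind of staff deliver both conditions: "All training and testing will be done by a physical therapist".

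The Data Analysis section has three steps.

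- **First session.** In a between-group parametric model, "we will compare baseline measures from both groups to post-training outcomes following the first training session".
- **Washout check.** Group A's device-off scores after the second session are compared with Group A's baseline "to confirm that the 60 minute break between training sessions allowed for a washout effect of the first training". No test, margin or decision rule is given.
- **Pooling.** This step opens "If we are able to confirm a washout effect" and continues "we will pool our data (n=30) to compare the outcome measures from baseline and post-training with the Walkasins turned on".

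The Hypotheses and Objectives section sets on against off. It predicts improvement with the device on and adds that "patients who wear Walkasins turned off will not improve their outcomes on gait and balance function".

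**The concern.** The pooled step is an uncontrolled before-and-after comparison inside a randomised cross-over. When the on score is taken, Group A has had one training session and one earlier round of testing, and Group B has had two of each. Familiarity with the tests and benefit from the therapist's training would raise the on score even if the device did nothing. The device-off post-training scores are the control for this. They will already be collected, but the pooled step does not use them.

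This is also the only step planned on all 30 subjects, so it is likely to give the smallest p-value and, if there is a practice gain, the largest estimate. An ineffective device could appear to work in this step, and a useful one would be overstated by the practice gain. The cross-over's main advantage, the precision of a within-subject on-versus-off comparison, would be lost.

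**Working it through.** **What each analysis estimates.** Let d be the device effect, p1 and p2 the practice and training gains present at the first and second post-training tests, and c any carry-over of on-training into Group A's off period.

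- Pooled step: [(p1 + d) + (p2 + d)] / 2 = d + (p1 + p2)/2.
- Washout check (Group A, off minus baseline): p2 + c.
- First-session comparison: (p1 + d) − p1 = d.
- Cross-over on minus off: [(p1 + d − p2 − c) + (p2 + d − p1)] / 2 = d − c/2.

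The pooled step carries the average practice gain in full. The cross-over contrast removes it, whether or not practice accumulates. The washout check sees only the sum p2 + c, so it cannot tell practice from carry-over.

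**Inputs.** N = 30, the two sequences and the three test occasions come from the documents. The documents give no alpha, SD, allocation ratio, practice gain or washout rule. Assumed here: 15 per sequence, two-sided 0.05, SD of the difference between any two FGA measurements 3 (range 2 to 4), and washout accepted if a paired t-test in Group A gives p ≥ 0.05. There is no stated figure to reproduce.

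**How often the washout check passes.** The standard error is 3/√15 = 0.775, so a 1-point shift is 1.29 standard errors. The exact noncentral-t pass rates for shifts of 0.5, 1, 1.5 and 2 points are 0.908, 0.775, 0.562 and 0.329. A 1-point carry-over with no practice passes equally often.

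**False positives with d = 0** (simulation, 60,000 trials per scenario, SD 3, p1 = p2). The pooled test has standard error 3/√30 = 0.55.

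| Practice gain (points) | Check passed | Passed, then falsely positive | Falsely positive among those passing | On-versus-off contrast, no check |
|---|---|---|---|---|
| 0.5 | 91% | 12% | 13% | 5% |
| 1 | 78% | 29% | 37% | 5% |
| 1.5 | 56% | 38% | 68% | 5% |
| 2 | 33% | 29% | 89% | 5% |

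For a 1-point gain, the rate of passing and then being falsely positive is 38% at SD 2 and 20% at SD 4. Among trials that pass it is 68% and 23%.

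If practice accumulates, the check blocks more:

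- gains of 0.5 then 1: 17% pass and are falsely positive;
- gains of 1 then 2: 20% (33% pass, and 61% of those are falsely positive);
- gains of 1.5 then 3: under 5%.

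**Bias with d = 2 and a 1-point gain.** The pooled step estimates 2 + (1 + 1)/2 = 3.0, or 2.9 among trials that pass the check. The cross-over contrast estimates 2.0.

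**Precision not used.** The standard error of the first-session change comparison is 3 × √(2/15) = 1.10. For the cross-over contrast it is half that, 0.55. With no carry-over, power for 2 points is 94% against 42% (45% with baseline adjustment). At SD 2 it is over 99% against 75%, and at SD 4 it is 75% against 26%.

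**The case against.** - **The damage is contained.** The first-session comparison is randomised, controls for practice, and is the only one for which the plan predicts significance. With no device effect, the chance that the washout check passes, the pooled test is positive and the first-session test also favours the device is under 1% in the scenarios tabulated. This stands: the flaw belongs to one step and not to the trial's evidence as a whole. But pooling does not depend on the first-session result, so the pooled result can be reported whatever that shows.
- **The rates depend on an assumed washout rule.** They do. Under an equivalence rule (90% confidence interval within a margin; SD 3, 1-point gain), the rate of passing and then being falsely positive is about 0.1% for a 1-point margin, 10% for 2 points and 30% for 3 points. The plan states no rule, so the figures show a range and are not a forecast.
- **The baseline comparator has a merit.** No on period precedes the on test in either sequence, so on-versus-baseline is free of carry-over from device-on training. The on-minus-off contrast is not, and the break is only 60 minutes within one visit. This is the most serious objection to the remedy, and the reason to keep the first-session comparison beside it.
- **The bias is small.** The modelled gains of 0.5 to 2 points compare with the 8-point FGA MCID quoted in the protocol. That figure is for vestibular disorders, and the plan does not use it as a success criterion. It predicts statistical significance, which a bias of this size can produce.

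**Conclusion.** The concern holds, with high confidence on the text. The pooled step uses baseline as its only comparator, and no on-versus-off within-subject analysis is planned anywhere. The bias equals the average practice and training gain. The washout check guards against it only in part: it uses about 15 subjects, has no stated criterion and cannot separate practice from carry-over.

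The magnitudes are less certain. With SD 3, non-significance taken as washout and equal gains of 0.5 to 2 points, 12% to 38% of trials of an ineffective device would pass the check and then show a false positive. A strict equivalence margin, or strongly accumulating practice, would bring this below 5%. All figures concern the FGA. The first-session comparison is unaffected, so this is an inexpensive improvement to one step and does not undermine the trial's main test.

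**What to change.** Replace the pooled baseline-versus-on comparison with the within-subject on-minus-off contrast in all 30 subjects, from a mixed model with condition, period and sequence as fixed effects and subject as random effect. The 4-Stage Balance Test, scored pass/fail by stage, needs an equivalent suited to its scale. Keep the first-session comparison of Group A with Group B as the carry-over-free analysis. Report both whatever the washout check shows, and state in advance which governs if they disagree. Present change from baseline descriptively only. Reword the hypothesis as on better than off, so that it no longer requires no improvement with the device off.

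The cost is analysis wording only, with no added visit, test or subject. The downside is carry-over. If half of a 2-point effect persists into Group A's off period (c = 1), the contrast falls to 2 − 1/2 = 1.5 points and power from 94% to 75% at SD 3 (98% at SD 2, 51% at SD 4). An after-effect in the opposite direction would inflate the contrast. The first-session comparison is exposed to neither.

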### **Risk to the Subjects and Approaches Taken to Minimize Risk:**

- Use of device/administration of physical stimuli - The device being tested may distract the subject while walking and increase the risk of falling. To prevent falling, a spotter will walk next to the subject to help regain balance if a fall starts to occur.
- Video recordings and photographs - We will take videos and photos of the person using the Walkasins for use in publications and presentations. There is a risk that their identity will be disclosed by being recognized in these publications and presentations. We will collect their separate consent for use of pictures and video.
- Use of medical records - We may use the medical records to obtain information related to the cause of their peripheral neuropathy, for example, to be used in describing subjects in the study. There is a risk that study personnel may inadvertently see other information in their medical record unrelated to their neuropathy that may be private in nature. We will obtain HIPAA authorization for use of the medical records.

PROTOCOL XXXX-X

The Effect of Walkasins on Balance and Gait in People with Peripheral Neuropathy

PI: [name]

Version Date: April 5, 2016

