## **Research Methodology:**

After enrollment into the study, subjects will complete a health screening questionnaire and the Activities-specific Balance Confidence Scale:

- Health Screening Questionnaire – Subjects will fill out a screening questionnaire to assess common health issues related to neurological, musculoskeletal, cardiopulmonary disorders, and other systemic diseases as well as information on falls and currently used medications.

PROTOCOL XXXX-X

[figure not shown]
The Effect of Walkasins on Balance and Gait in People with Peripheral Neuropathy

PI: [name]

Version Date: April 5, 2016

- Activities-Specific Balance Confidence (ABC) Questionnaire – Powell and Myers (1995) developed the Activities-Specific Balance Confidence (ABC) Scale in an effort to detect levels of balance confidence in elderly persons (see Appendix). The ABC scale is a one-page questionnaire that asks questions about balance confidence when performing 16 different tasks.

Subjects will then don the Walkasins device and complete baseline measures of the Functional Gait Assessment (FGA), 10 meter Gait Speed and 4-Stage Balance Test (see Figure 2 for protocol design). During baseline testing, the Walkasins will be turned off.

**Figure 2:** Cross-over study design.

- Functional Gait Assessment – The FGA is a reliable and valid measure of gait function related to postural stability and has been shown to be effective in classifying fall risk in older adults and predicting unexplained falls in community-dwelling older adults (Wrisley, Marchetti et al. 2004; Wrisley and Kumar 2010). It has also been validated in stroke survivors (Lin, Hsu et al. 2010) and patients with Parkinson’s disease (Leddy, Crowner et al. 2011) and it has less flooring and ceiling effect than the Dynamic Gait Index (Lin, Hsu et al. 2010). The FGA includes a 10 item scale where each item is scored from 0 to 3 (3=normal, 2=mild impairment, 1= moderate impairment, 0 = severe impairment). The maximum score is 30. A difference of 8 points between measurement times is defined as the MCID in persons with vestibular disorders (Marchetti and Whitney 2010).

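### The protocol names falling as a device risk but does not describe recording falls, losses of balance or spotter contacts with the device on and off

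*Combined protocol and SAP*

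**What the plan says.** The section on risk to subjects lists one physical harm: "The device being tested may distract the subject while walking and increase the risk of falling". The safeguard follows directly: "To prevent falling, a spotter will walk next to the subject to help regain balance if a fall starts to occur". The other two risks in that section concern images and medical records.

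Data Analysis lists the outcomes: "The primary outcome measures of this study include the Functional Gait Assessment, 10 meter Gait Speed test, and the 4-Stage Balance Test". No safety measure is among them.

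Research Methodology describes the scoring. For the Functional Gait Assessment (FGA), "The FGA includes a 10 item scale where each item is scored from 0 to 3". For walking, "Gait speed (10 meter walk using the middle 6 meters) will be assessed under two conditions", namely normal and fastest speed. For the 4-Stage Balance Test, "Subjects pass if they can hold the stance for 10 s and then move on to the next stance". None of these descriptions mentions a trial in which the spotter stepped in.

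The one place where fall data are collected is the health screening questionnaire, which covers "other systemic diseases as well as information on falls and currently used medications". Subjects complete it before they put on the device for baseline testing.

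**The concern.** The Introduction presents the device as an answer to the need to manage fall risk. The harm named in the risk section is the reverse of that benefit, so it is the safety result a reader will most want to see. A higher FGA score or a faster walk with the device on could come with more rescues by the spotter, and the planned outcomes would show only the gain.

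Such events are plausible. Subjects report balance difficulty and enter with an FGA below 23 or a failed early stance. Their usual assistive devices are not allowed during the study, and one walk is at maximum speed.

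There is also a measurement question. A speed timed over 6 m with a hand on the subject is not the same quantity as an unaided speed, and the plan does not tell them apart. No masking of the therapist to device state is described, so the amount of help could vary with knowledge of the condition.

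**Working it through.** No figure in the protocol is in dispute. The sample size of 30 is given without power, effect size or allocation ratio, so it cannot be reproduced, and this point does not depend on it. Steps 2 to 5 are illustrations. Event rates and shares helped are assumed, as is an equal split of 15 per group.

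**1. What is collected, and when.**
- Before baseline: questionnaire, including fall history.
- Baseline (off), then two periods (on then off, or off then on): FGA, gait speed and 4-Stage test.
- During any of these: no described record of a fall, loss of balance or spotter contact.

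The number of events by condition is therefore not available from the planned data. The study is one visit of 2 to 3 hours, so there is no later occasion to collect it. Video is taken for publications and presentations, with no stated use for counting events.

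**2. What a count could show if nothing happened.** With zero events in n subjects, the one-sided 95% upper bound is 1 − 0.05^(1/n).
- n = 30: 1 − 0.05^(1/30) = 9.5%.
- n = 15: 1 − 0.05^(1/15) = 18.1%.

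The two-sided exact bounds, 1 − 0.025^(1/n), are 11.6% and 21.8%.

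**3. Chance of seeing at least one event in 30.** This is 1 − (1 − p)^30 for an assumed per-subject rate p.
- p = 5%: 78.5%.
- p = 10%: 95.8%.
- p = 20%: 99.9%.

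**4. Power to compare event rates, 15 v 15, two-sided 0.05.** Normal approximation: power = Φ{[d − 1.96√(2p̄(1 − p̄)/15)] / √[(p₁(1 − p₁) + p₂(1 − p₂))/15]}, where d = p₁ − p₂ and p̄ is the mean of the two rates.
- 30% v 10%: 27%.
- 40% v 10%: 47%.
- 50% v 10%: 68%.

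The counts should therefore be described, not tested.

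**5. Possible size of bias in the performance outcomes.** Bias in a mean = (share helped on − share helped off) × (error per helped trial).
- *Gait speed.* For the bias to reach the 0.10 m/s that the protocol gives as clinically important, a difference in help of 10 to 30 percentage points would need an error per helped walk of 0.10/0.10 = 1.0 m/s down to 0.10/0.30 = 0.33 m/s.
- *FGA.* Suppose one helped item per subject is credited 1 to 3 points that it should not have. The bias is then 0.10 × 1 = 0.1 to 0.30 × 3 = 0.9 points. The protocol cites 8 points as clinically important, from vestibular disorders. This case arises only if the instrument's own criteria let a helped item score above 0, which the protocol does not show.

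The sign follows the difference in help. More help with the device on favours the device if help raises the score; more help with it off does the opposite.

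**The case against.** The strongest reply is that this is a modest reporting gap. The study is a single short visit by 30 subjects, a physical therapist does the testing, and counts would have too little power for a comparison. Some material is absent from the public copy, and site forms or procedures may already capture such events. These limits stand, and the point is confined to what the available text describes. They do not remove the point: descriptive counts by condition are still informative, and without them no rate can be stated.

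Three stronger readings are tempting, and the documents do not support them.

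- *That a stance held with help would count as a pass.* In a group of 15, one such stance would move the pass rate by 1/15 = 6.7 points. But the pass rule requires the subject to hold the stance, which implies an unaided hold. The spotter is described only for walking: "a spotter will walk next to the subject to help regain balance if a fall starts to occur".
- *That the outcomes are flattered.* This assumes more help with the device on. The spotter provision does not differ by condition, so the direction is unknown.
- *That helped FGA items escape a low score.* The protocol summarises the 0 to 3 scale but does not reproduce the item criteria, which may already deal with loss of balance or assistance.

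A further caution concerns the remedy. Declaring helped walks invalid could remove the worst walks with the device on, and so create the bias that the change is meant to prevent.

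**Conclusion.** The point holds as a gap in data collection. The protocol names an increased risk of falling while walking and provides for physical help, but the available text describes no record of in-session falls, losses of balance or spotter contacts. The trial as written can give no on or off rate for its one named physical harm.

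The effect on the performance outcomes is secondary. It is clearest for gait speed, where nothing separates a helped walk from an unaided one. It requires help to differ between conditions, and it could run either way. Under the assumed differences in help, it is likely to be small beside the thresholds the protocol cites unless helped walks are badly distorted. The change is worth making because the information costs almost nothing to collect on the day and may not be recoverable afterwards.

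**What to change.** 1. Record each fall, loss of balance and spotter contact by subject, test and condition (baseline, on, off).
2. Report paired on-versus-off counts descriptively beside the primary outcomes, with exact confidence limits and no hypothesis test.
3. Score FGA items and 4-Stage stances by the instruments' own criteria, and state in advance that this is the rule when the spotter has helped.
4. Keep any helped walk in the main analysis and flag it; do not drop it.
5. Specify one sensitivity analysis in which helped trials take the worst outcome: an FGA item at 0, a stance failed, and a walk at the slowest speed observed in the study for that instruction.

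The cost is a small addition to data recording and one table. Sample size, visits, staff and tests do not change.
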